10.4.9 Multiple Comparison/Multiplicity

Not applicable as there is one primary efficacy endpoint.

10.4.10 Tabulation of Individual Response Data

Individual participant data will be listed by measure and time point.

10.4.11 Exploratory Analyses

Exploratory analyses for ancillary endpoints (not primary or secondary endpoints), with rationale, are as follows:

-Mean systolic blood pressure (BP) at 3-month follow-up visit. Adequately controlled BP is an important component of secondary prevention for patients with IHD, and may be influenced by participation in mHealth-CR (mediated by direct effects of exercise, as well as by feedback from weekly home BP measurement which may influence medication management and adherence). Rather than determining a threshold for optimal BP control, which remains an area of debate, we will compare mean systolic BP in the intervention versus usual care groups at 3 months.

-Frailty. Frailty is a syndrome of increased physiologic vulnerability to stressors. In older adults with IHD,

CONFIDENTIAL

This material is the property of the NYU School of Medicine and Langone Medical Center. Do not disclose or use except as authorized in writing by the study sponsor

frailty is common and associated with a range of adverse outcomes. We will measure frailty at baseline and 3 months using the criteria described by Fried et al: unintentional weight loss (≥ 10 pounds), weak grip strength (measured by handheld dynamometer), exhaustion, slow gait, and low physical activity. Participants meeting 3/5 of these criteria will be classified as frail. Since mHealth-CR may mechanistically modulate the frailty phenotype by building muscle mass and promoting physical activity, we will analyze the number of participants in each group that transition from “frail” to “not frail” between baseline and 3 months.

-Attendance at traditional (ambulatory) CR. We will ask participants at 3 months whether they have attended ambulatory CR. Based on the study protocol, all participants will receive a referral to ambulatory CR at time of discharge. We will therefore examine the rates of attendance (rather than rates of referral) between participants in the intervention versus usual care arms. Since participants may not recall the number of sessions attended, we will count number of sessions via electronic health record (EHR) review.

-Change in depressive symptoms (PHQ-8) (baseline to 3 months). Depression is common among IHD patients and associated with poor outcomes. While baseline depressive symptoms may determine engagement (to be evaluated in Aim 5), participation in mHealth-CR may also influence subsequent depressive symptoms. The PHQ-8 is a commonly used screen for depressive symptoms that is publicly available, easy to administer, and has been used to assess responsiveness to therapy. For our analysis, we will analyze mean change in PHQ-8 score from baseline to 3 months (intervention versus usual care

A PHQ-8 score of 10 or greater is suggestive of major depressive disorder (MDD), while a score of 20 or greater is suggestive of severe major depressive disorder. Study participants with a score of 10 or greater will be asked if they are already in treatment for depressive symptoms (defined as prescribed antidepressant medication or in active counseling.) If the subject is not in treatment, we will ask for their consent to notify their primary care provider or cardiologist about the result of the screening questionnaire.

-Barriers to and facilitators of participation from qualitative interviews (subsample of participants). The ancillary endpoint of barriers to, and facilitators of, participation will be collected through focus groups, which will be conducted with a purposive sampling of participants (8-10 per category) across levels of engagement (e.g., sustained engagement, disengagement, reengagement, deteriorating engagement).⁸³ To optimize recruitment success, we will identify members of each group through interim data analyses. Participants will be eligible after the 3 month visit is complete. Depending on engagement patterns, questions will include topics such as reasons for change in mHealth use, features that influenced engagement, perceived satisfaction, ease of use, and recommended changes to sustain engagement. Each group will last one hour, and will be audiotaped. [name] (Co-I) will conduct all focus groups using a semi-structured moderator's guide that will include structured prompts to elicit themes. Interviews will be transcribed verbatim and coded using Atlas.ti software.

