3.2 Secondary Objectives

The *secondary efficacy objectives* are to evaluate whether mHealth-CR improves the endpoints of (1) goal attainment, as measured by goal attainment scaling (GAS); (2) health status (general and disease-specific); (3) basic and instrumental activities of daily living (ADLs); (4) hospital readmission; and (5) death, in participants receiving mHealth-CR versus usual care.

The *ancillary efficacy objectives* are to assess whether mHealth-CR improves the quantitative endpoints of (1) mean systolic blood pressure at 3-month follow-up visit; (2) change in frailty status; (3) attendance rate at traditional (ambulatory) CR; (4) change in PHQ-8 depression score (baseline to 3 months).

4 Study Design and Endpoints

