4.2.3 Exploratory Endpoints

Ancillary endpoints include: (1) mean systolic BP at 3 months; (2) change in frailty status; (3) attendance at traditional CR; (4) change in depressive symptoms (PHQ-8); (5) barriers to and facilitators of participation from qualitative interviews (subsample of participants).

Ancillary endpoints (*systolic BP, change in frailty status, traditional CR attendance, change in depressive symptoms*) will be measured at the baseline visit, at-home (for intervention group), and at 3-month follow-up visit. Home BP in the intervention arm will be measured with a digital blood pressure cuff provided to participants, which synchronizes with our mHealth-CR software. Frailty will be assessed using the Fried criteria (unintentional weight loss, weakness, exhaustion, slow gait, low physical activity);⁸² we will analyze the number of participants in each group who transition from “frail” to “not frail” between baseline and 3 months. For attendance at traditional CR, we will measure (for each participant) whether traditional CR attended (yes/no), date of first traditional CR visit, number of days from hospital discharge to first traditional CR visit, and total number of traditional CR sessions attended.

The System Usability Scale (SUS) will be used to measure the usability of technology and software in intervention arm participants at the 3-month follow up visit. The SUS is a 10-item questionnaire with five response options ranging from “Strongly Agree” to “Strongly Disagree”. This questionnaire will be administered by the Research Coordinator during the 3-month follow-up visit and open ended feedback will be solicited from the intervention arm subjects

5 Study Enrollment and Withdrawal

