7.1 Study Procedures/Evaluations

7.1.1 Study Specific Procedures

Study procedures can be seen in Table 1.

Table 1. Schedule of Study Activities

	Baseline	Weekly	Ambulatory follow-up
Study Week (approximate)	0	1-12	12
Informed Consent	X		
Demographics	X		
Height	X		
Weight and Blood Pressure	X		X
6 Minute Walk Test	X		X
Short Form 12 (SF-12)	X		X
Seattle Angina Questionnaire 7 (SAQ-7)	X		X
Activities of Daily Living (ADLs)	X		X
Mini-Cog	X		
Goal Attainment Scaling (GAS)	X		X
Depression (PHQ-8)	X		X
Frailty Elements	X		X
Chart abstraction (comorbidities, medications, laboratory/cardiac test results)	X		
Randomization	X		
Education on cardiac risk factor management	◊		
Ascertainment of home environment and barriers to mobility	◊		
Introduction to mHealth-CR software	◊		
Personalized exercise plan	◊		
Daily passive activity monitoring (Fitbit)		◊	
Daily therapist-directed activity (walking, upper extremity resistance training)		◊	
Daily mHealth data entry		◊	
Weekly exercise therapist phone call		◊	

CONFIDENTIAL

This material is the property of the NYU School of Medicine and Langone Medical Center. Do not disclose or use except as authorized in writing by the study sponsor

Weekly blood pressure measurement		◊	
Weekly video education		◊	
Hospital readmissions (questionnaire)			X
Chart abstraction (hospital readmission verification, attendance at traditional CR)		Week 8	X
		Biweekly/ Monthly	
Phone assessment of ADLs		X	

X = All participants ◊ = Intervention participants only

CONFIDENTIAL

This material is the property of the NYU School of Medicine and Langone Medical Center. Do not disclose or use except as authorized in writing by the study sponsor

- *Chart Abstraction* will be performed by the research coordinator. Elements will be entered into a secure Research Electronic Data Capture (REDCap) database created by NYU DataCore.
 - Medical history/comorbidities: hypertension, diabetes, heart failure, peripheral artery disease, atrial fibrillation, cancer, chronic lung disease, obesity, chronic kidney disease, chronic liver disease, gastrointestinal bleeding, cerebrovascular disease, dementia, osteoarthritis, tobacco use, alcohol use.
 - Outpatient medications.
 - Laboratory data: hemoglobin, platelet count, white blood cell count, sodium, potassium, BUN, creatinine, glucose, troponin (all based on admission blood draw). Peak troponin value will also be abstracted.

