- *3-month ambulatory assessment (all participants).* The research coordinator will schedule an ambulatory visit to take place 3 months after the baseline assessment. For NYU patients, this visit will occur at a designated research space in the main hospital campus (NYU Tisch Hospital). For participants at NYULH-Winthrop, the visit will be performed at the outpatient office of the FGP of Winthrop Cardiology Associates located at [name]. For UMMHC patients, this visit will take place at the Ambulatory Care Center (1st floor) at [name]. For participants at the Bellevue site, the CTSI Bellevue research suites or designated areas in the NYU main hospital campus will be used. For Yale patients, this visit will take place at ambulatory space adjacent to Yale-New Haven Hospital. The estimated time for the 3-month visit is 1 hour. Measures at 3 months will include a repeat of several baseline instruments to evaluate change over time (weight, BP, SF-12, SAQ-7, ADLs, PHQ-8). Participants will also be asked about hospital readmissions since time of last visit. 6MWT and Goal Attainment Scaling will be performed by the research nurse and/or a blinded assessor.

The Fitbit, portable tablet computer, and BP cuff will be collected. The research coordinator will also perform chart abstraction at 3-months to evaluate ambulatory CR attendance, and to verify self-report of hospital readmissions. For readmissions that occur outside the NYU, Bellevue, UMass or Yale systems, hospital records will be obtained.

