7.2.2 Enrollment/Baseline

Enrollment/Baseline Visit (Visit 1, Day 1)

- Obtain informed consent of potential participant verified by signature on study informed consent form.
- Verify inclusion/exclusion criteria.
- Obtain demographic information, medical history, medication history, comorbidities, and laboratory/cardiac test results.
- Obtain height and weight.
- Record blood pressure.
- Administer study assessments:
 - 6-minute walk test. Standard protocol including vital signs measurement pre- and post-testing.
 - Frailty elements: Unintentional weight loss (≥ 10 pounds in past 1 year), weak grip strength (measured by handheld dynamometer), exhaustion (measured by two questions from CES-D scale), slow gait (measured in meters/second over a 15-foot walk), and low physical activity (measured by kilocalories per week expended).
- Conduct questionnaires:
 - SF-12
 - SAQ-7
 - ADLs
 - Mini-Cog
 - PHQ-8
 - GAS
- (Intervention Participants only):
 - Provide participants with tablet computer
 - Receive FitBit wearable activity monitor and BP cuff monitor
 - Education on cardiac risk factor management (in person or remote)
 - Ascertainment of home environment and barriers to mobility (in person or remote)
 - Introduction to the mHealth-CR software
 - Personalized exercise plan: Participants will be instructed by the exercise therapist to use mHealth-CR for at least 5/7 days each week. Training will include education on BP cuff use.
- All participants will be instructed to participate in phone calls with the research coordinator to complete ADL assessments.

CONFIDENTIAL

This material is the property of the NYU School of Medicine and Langone Medical Center. Do not disclose or use except as authorized in writing by the study sponsor

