10.4.2 Analysis of the Primary Efficacy Endpoint(s)

6MWD

We will assess the difference in 6MWD by calculating difference scores for each participant and comparing the intervention and usual care groups with an independent group t-tests allowing for unequal variances. We will also regress 3-month 6MWD on a binary indicator of treatment group, with adjustment for baseline 6MWD and the stratification factor (enrollment site). While randomization should obviate the need for additional adjustment, we will explore whether adjustment for participant-level characteristics (e.g., demographic factors or referral to ambulatory CR) is necessary, using the change-in-estimate criterion. We realize that engagement with the mHealth-CR program may also affect attendance and engagement with structured ambulatory CR programs. We intend to explore this as a mediator of the effect of assignment to the intervention arm. We will use structural equation models to estimate the direct and indirect effects of mHealth, where the direct effect is that of mHealth-CR on the 6MWD, and the indirect effect is mediated through attendance at structured ambulatory CR.

Engagement

We hypothesize that (1) among participants offered mHealth-CR, there will be distinct trajectories of engagement (e.g., sustained engagement, disengagement, reengagement, deteriorating engagement); and (2) there will be significant differences in participant characteristics among these groups. While our aim is largely exploratory (given the paucity of data on mHealth-CR engagement), we will test whether the following characteristics are significant: age (≥ 80 years), sex, race/ethnicity, comorbidity burden (≥ 2 chronic medical conditions), frailty, social support (based on living alone), cognitive impairment (based on Mini-Cog), and depressive symptoms (based on PHQ-8). We selected these factors based on literature related to engagement in other technologies. We will conduct latent class analysis to identify profiles of engagement and explore whether these factors indicate membership in a class; these models use maximum likelihood estimation,

CONFIDENTIAL

This material is the property of the NYU School of Medicine and Langone Medical Center. Do not disclose or use except as authorized in writing by the study sponsor

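### Section 10.4.11 compares 3-month systolic blood pressure without using the recorded baseline value: the comparison is valid, but it gives up precision that is free to recover

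*Combined protocol and SAP*

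**What the plan says.** Section 3.2 lists the ancillary endpoint as "mean systolic blood pressure at 3-month follow-up visit", and section 10.4.11 gives its analysis in one clause: "we will compare mean systolic BP in the intervention versus usual care groups at 3 months". Neither place names a baseline covariate, a change score, a test or a model.

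The baseline value is collected. Section 4.2.3 says that the ancillary endpoints, systolic pressure among them, "will be measured at the baseline visit, at-home (for intervention group), and at 3-month follow-up visit". Table 1 in section 7.1.1 marks the row "Weight and Blood Pressure" for all participants at baseline and at follow-up. The baseline visit list in section 7.2.2 includes "Record blood pressure". The description of the 3-month visit in section 7.1.1 calls its measures a "repeat of several baseline instruments to evaluate change over time (weight, BP, SF-12, SAQ-7, ADLs, PHQ-8").

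Other continuous outcomes do use their baseline. The 6MWD regression in section 10.4.2 is "with adjustment for baseline 6MWD and the stratification factor (enrollment site"). Section 10.4.3 adjusts 3-month health status for its baseline level. For depressive symptoms, section 10.4.11 says "we will analyze mean change in PHQ-8 score from baseline to 3 months".

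**The concern.** Blood pressure is repeated in order to assess change, yet the stated analysis looks only at the 3-month level. Two things follow. First, variation between participants that was already visible at baseline stays in the error term, so the confidence interval is wider than it needs to be. Second, with about 80 evaluable controls, the arms can differ by chance in baseline pressure, and part of that difference reappears in the 3-month comparison.

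Nothing elsewhere in the plan fills the gap. The general approach in section 10.4.1 foresees a look at baseline balance but prescribes no covariates. The change-in-estimate rule in sections 10.4.2 and 10.4.3 covers the primary and secondary models, depends on the data, and does not name baseline systolic pressure.

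**Working it through.** **Inputs from the documents (section 10.5).** 240 intervention and 80 usual care participants evaluable; two-sided 0.05.

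**Assumed inputs, because the documents give none for systolic pressure.** SD 18 mmHg (range 15 to 20), equal at both visits; rho from 0.2 to 0.6; a difference of 6 mmHg for the power illustration.

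**Step 1: check the sample size inputs on the plan's own figure.** Section 10.5 states about 90% power for 25 m and 80% for 22 m, with SD 60 m.
- SE = 60 × sqrt(1/240 + 1/80) = 60 × 0.1291 = 7.75 m.
- Power for 25 m = Φ(25/7.75 − 1.96) = 89.8%; for 22 m it is 81.1%. Both agree with the plan.

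**Step 2: size of a chance baseline difference.** SE = 0.1291 × SD, which is 2.32 mmHg at SD 18 (1.94 at SD 15, 2.58 at SD 20). In simulation at SD 18, a gap of 4 mmHg or more in either direction arose in about 8-9% of trials. The part expected to carry into the unadjusted 3-month difference is rho times the gap. For a 4 mmHg gap that is 0.2 × 4 = 0.8 mmHg at rho 0.2, and 0.6 × 4 = 2.4 mmHg at rho 0.6.

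**Step 3: gain from adjustment at SD 18.**
- SE(adjusted) = SE(unadjusted) × sqrt(1 − rho²)
- Equivalent unadjusted total N = 320/(1 − rho²)
- Power = Φ(6/SE − 1.96)

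| rho | Variance cut | SE (mmHg) | 95% CI half-width (mmHg) | Equivalent N | Power for 6 mmHg |
|---|---|---|---|---|---|
| unadjusted | – | 2.32 | 4.55 | 320 | 73% |
| 0.2 | 4% | 2.28 | 4.46 | 333 | 75% |
| 0.3 | 9% | 2.22 | 4.34 | 352 | 77% |
| 0.5 | 25% | 2.01 | 3.94 | 427 | 85% |
| 0.6 | 36% | 1.86 | 3.64 | 500 | 90% |

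The variance cut and the equivalent N do not depend on the SD. Over SD 15 to 20 the unadjusted half-width is 3.80 to 5.06 mmHg, and at rho 0.5 the adjusted one is 3.29 to 4.38 mmHg.

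**Step 4: simulation check.** There were 20,000 trials per rho at SD 18 with no treatment effect. At rho 0.3 and 0.5 the empirical SEs were 2.31 against 2.20 and 2.33 against 2.03 (unadjusted against adjusted). The unadjusted estimate correlated with the baseline gap at 0.31 and 0.49, the adjusted one at about 0. Both estimators averaged essentially zero error.

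**Step 5: change scores.** With equal SDs, the variance of a change-score comparison relative to the unadjusted 3-month comparison is 2(1 − rho). Below rho 0.5 this exceeds 1, so moving systolic pressure to a plain change score could lose precision. The adjusted variance relative to the change-score variance is (1 − rho²)/[2(1 − rho)] = (1 + rho)/2. For PHQ-8 that would mean 35% lower variance at rho 0.3 and 20% lower at rho 0.6.

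**The case against.** The strongest reply is that this is not an error. Comparing 3-month means between randomized arms is valid, and the endpoint is ancillary. The sentence in section 10.4.11 is a brief description that contrasts a mean with a control threshold. It does not exclude covariates, and the balance check in section 10.4.1 would show a baseline gap. All of this stands. The point is one of efficiency and of stating the model in advance.

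The reply is also right that the gain may be small. Section 5.1 allows the baseline visit in hospital or at an ambulatory visit within 4 weeks, and section 7.2.4 puts follow-up at day 90 with 30 days allowed after. Correlation across such different settings could be modest, and at rho 0.2 the variance gain is only 4%.

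Three stronger readings are tempting, and the documents do not support them:
- A reader might infer that a chance baseline gap passes whole into the result. Only the fraction rho does; full carry-over would need rho of 1.
- A reader might infer that the planned PHQ-8 change score is wrong. Change is that endpoint as defined, and comparing change between randomized arms is also unbiased. The case for adjustment there is precision alone.
- A reader might infer that home readings, taken in the intervention arm only, could enter the comparison. Section 3.2 already ties the endpoint to the follow-up visit, where all participants are measured.

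**Conclusion.** The point holds as a no-cost improvement of low severity. The plan collects baseline systolic pressure in both arms, states no use for it in the between-arm analysis, and adjusts for baseline in the 6MWD regression and in the health status analysis. Adjustment would cut the variance by rho squared, between 4% and 36% over rho 0.2 to 0.6. The power range of 75-90% against 73% rests wholly on the assumed SD, rho and 6 mmHg; the trial set no power goal for this endpoint, so no stated target is missed. A reader might go further and infer systematic bias or an inflated type I error, but neither follows from the planned comparison. The primary conclusion is unaffected.

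**What to change.** In section 10.4.11, state that 3-month visit systolic pressure will be analysed by linear regression on treatment, baseline systolic pressure and enrollment site, the same form as the 6MWD regression in section 10.4.2. Report the adjusted difference with its 95% confidence interval. Do not substitute a plain change score.

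Optionally, use the same form for PHQ-8, with the 3-month score as outcome and the baseline score as covariate. Under equal variances this is at least as precise as the planned comparison of raw change.

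The cost is a sentence or two of SAP wording, best added before the outcome data are examined. No new measurement, visit or participant is needed.

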10.5 Sample Size

We will randomize 400 participants using a 3:1 allocation, resulting in 300 participants in the intervention group and 100 participants in the usual care group. While we will aim to minimize participant dropout, we include adjustment for up to 20% dropout in each arm, resulting in about 320 participants with evaluable endpoints (240 intervention, 80 usual care). We wish to be able to detect a clinically meaningful difference between groups in our primary efficacy endpoint, change in 6MWD from baseline to 3 months. A recent meta-analysis⁵⁷ found an average difference in 6MWD of about 60 meters before and after traditional CR. Perera et al. determined this degree of change in 6MWD to be clinically meaningful based on its relationship to other health status measures.⁹⁸ Minneboo et al., however, also estimated an improvement in 6MWD in a control group of approximately 35 meters.⁵⁹ We therefore require adequate power to detect a difference between groups of less than 25 meters in change in 6MWD (i.e., the difference between a 60-meter improvement in the intervention group and a 35-meter improvement in the usual care group); this is the same amount estimated by Gremeaux et al. as a minimal clinically important difference in patients with IHD.⁹⁹ Assuming a conservative standard deviation estimate of 60 meters,⁵⁷ 320 participants provide approximately 90% power to detect a difference between groups of 25 meters, using a two-sided, 0.05-level test; there is 80% power to detect a difference

CONFIDENTIAL

This material is the property of the NYU School of Medicine and Langone Medical Center. Do not disclose or use except as authorized in writing by the study sponsor

between groups as small as 22 meters. This sample size also provides at least 80% power to detect reasonable effect sizes in secondary endpoints.

While the sample size was determined to provide sufficient power to detect a clinically meaningful difference in the primary outcome of 6MWD, it enables comparisons of secondary efficacy endpoints as well. The table below shows clinically meaningful effect sizes for these outcomes, and gives the power to detect these effect sizes

CONFIDENTIAL

This material is the property of the NYU School of Medicine and Langone Medical Center. Do not disclose or use except as authorized in writing by the study sponsor

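### The ancillary frailty endpoint is analysed in one direction only, so new frailty is never compared between arms, and the denominator for recovery is not stated.

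*Combined protocol and SAP*

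**What the plan says.** Section 3.2 lists "2) change in frailty status" among the ancillary efficacy objectives, and section 4.2.3 repeats it as an ancillary endpoint. Neither gives a direction.

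The analysis is described twice in nearly the same words. Section 4.2.3 has "we will analyze the number of participants in each group who transition from" frail to not frail, and section 10.4.11 has "we will analyze the number of participants in each group that transition from" frail to not frail, in both cases between baseline and 3 months. The classification rule in section 10.4.11 is "Participants meeting 3/5 of these criteria will be classified as frail". Neither section states a denominator, an effect measure or a test specific to frailty.

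Table 1 in section 7.1.1 schedules the frailty elements for all participants at baseline and at the ambulatory follow-up. On sample size, section 10.5 says "We will randomize 400 participants using a 3:1 allocation, resulting in 300 participants in the intervention group and 100 participants in the usual care group", with 20% dropout "resulting in about 320 participants with evaluable endpoints (240 intervention, 80 usual care").

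**The concern.** Change in frailty status can go either way, but the planned measure sees only recovery. Participants not frail at baseline cannot register an event, so the analysis cannot show whether the intervention prevents or provokes frailty in them. Two arms with the same recovery would look alike even if one had clearly more frailty at 3 months. The rationale in section 10.4.11 (muscle mass and physical activity) applies to preventing onset as much as to reversing it.

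The second gap is the denominator. Recovery can occur only in those frail at baseline, and neither section says that this is the group over which it will be expressed. With three times as many participants on intervention, a bare number per arm would be uninformative.

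**Working it through.** **Inputs from the documents.** Section 10.5: 400 randomised 3:1, 20% dropout in each arm.

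- 400 × 3/4 = 300 and 400 × 1/4 = 100.
- 300 × 0.8 = 240 and 100 × 0.8 = 80, total 320. This reproduces the plan's evaluable numbers.

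The plan states no prevalence, rate or power for frailty, so there is no frailty figure to reproduce.

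**Assumed inputs.** Baseline frailty f = 20% (range 10% to 40%); recovery r = 30% in both arms; new frailty i = 15% on intervention and 5% on usual care. These are for illustration and do not come from the documents.

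**Who can contribute.** Frail at baseline = n × f: 240 × 0.20 = 48 and 80 × 0.20 = 16. Not frail at baseline: 192 and 64. The planned measure is silent on 1 − f of the sample, which is 80% here and 90% to 60% over the range.

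**What the planned measure shows.** Recoveries = n × f × r: 48 × 0.30 = 14.4 and 16 × 0.30 = 4.8. As a proportion of those frail at baseline this is 30% v 30%, no difference. As a bare number it is threefold higher on intervention, purely from the allocation.

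**What happened to frailty.** Prevalence at 3 months = f(1 − r) + (1 − f)i.

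- Intervention: 0.20 × 0.70 + 0.80 × 0.15 = 0.14 + 0.12 = 26%.
- Usual care: 0.20 × 0.70 + 0.80 × 0.05 = 0.14 + 0.04 = 18%.

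| Assumed baseline frailty | Frail at 3 months, intervention | Frail at 3 months, usual care | Recovery among baseline frail |
|---|---|---|---|
| 10% | 20.5% | 11.5% | 30% v 30% |
| 20% | 26% | 18% | 30% v 30% |
| 30% | 31.5% | 24.5% | 30% v 30% |
| 40% | 37% | 31% | 30% v 30% |

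The gap is (1 − f) × 10 percentage points, 6 to 9 points over this range, and the planned measure shows none of it. The blind spot is symmetric. With the two onset rates exchanged, frailty at 20% prevalence would be 18% v 26% in favour of the intervention, and that benefit would be missed too.

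**The case against.** A reader might infer that the plan will set raw counts from a 3:1 trial side by side, so that a threefold excess would pass for an effect. The documents do not support that. Section 4.2.2 uses the same kind of wording, a number of participants, for residual angina, and the table in section 10.5 powers that outcome as a difference of 15-20%. Section 10.4.1 calls for two-sided tests and confidence intervals, and the missing-data paragraph of section 10.6.1 requires denominators with every summary. What remains is narrower. The denominator rule is there to show missing values, and it does not make the baseline-frail group the denominator for recovery.

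A reader might also infer that the trial is blind to functional decline. It is not: change in 6MWD is the primary endpoint, and section 4.2.2 defines the ADL endpoint to include worsening. Nor is baseline frailty otherwise unused, since section 10.4.2 names it as a candidate predictor of engagement class. Individual listings are planned (section 10.4.10), but a listing is not a comparison between arms.

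Low power is not the defect. With 20% frail at baseline and recovery of 50% v 30%, power is about 27% or 31% depending on the variance formula, but those rates are assumed and the plan claims no power for frailty.

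Finally, reversal is a reasoned choice for an exploratory endpoint. That is fair, and it keeps the point small. It does not explain why an endpoint named as change omits one direction.

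**Conclusion.** The point holds as a minor one. Sections 4.2.3 and 10.4.11 agree with each other and restrict the comparison to frail-to-not-frail transitions. No section plans a comparison of onset, and the at-risk denominator is not stated. These conclusions rest on the text alone.

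The size rests on assumed rates: 26% v 18% frail at 3 months with equal recovery is an illustration of what the measure could miss, not a forecast. The threefold ratio of bare numbers needs only the 240:80 split together with equal baseline frailty and recovery, and it would mislead only if numbers were reported without the right denominator. The sample size and all primary and secondary conclusions are unaffected.

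**What to change.** In sections 4.2.3 and 10.4.11:

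1. Compare frailty at 3 months between arms in all participants with data, either as frail yes/no (logistic regression) or as the criteria count (ordinal regression), adjusted for baseline frailty and site.
2. Report both transitions as percentages of those at risk in each arm: recovery among those frail at baseline, onset among those not frail at baseline.

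Before a 0-5 count is used, reconcile the data-collection text. The coordinator assessment in section 7.1.1 lists four elements and omits low physical activity, while sections 7.2.2 and 10.4.11 list five. The 3-month assessment paragraph in section 7.1.1 does not name frailty among the repeated measures, while Table 1 does. The sponsor should confirm that all five criteria are collected at both visits. The weight-loss criterion looks back one year (sections 7.1.1 and 7.2.2), so at 3 months it still covers about nine months before baseline. That limits the planned measure and the replacement alike.

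The cost is revised wording and a little extra exploratory analysis. If all five criteria are confirmed as collected at both visits, no new data are needed.
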